10.0 DRUG INFORMATION

10.1 Varenicline Tartrate (Chantix®; Champix®)

Varenicline (Chantix™) is minimally metabolized by the liver, and 92% is excreted by the kidney unchanged.

Varenicline tartrate (Chantix™) is a nicotinic receptor partial agonist that binds with high affinity and selectivity at the $\alpha 4\beta 2$ neuronal nicotinic acetylcholine receptors.

Procurement

Varenicline and matching placebo will be provided by Pfizer Inc. and shipped by the Alliance Research Base Pharmacy.

“Varenicline” and “Placebo” will be supplied as 0.5 mg tablets for oral administration. Bottles will be labeled as “Varenicline or Placebo” so that the local investigators will be blinded as to the actual contents of the bottles.

After receiving IRB approval for this study, each participating institution will order a starter supply of varenicline/placebo from the Alliance Research Base Pharmacy by faxing the Alliance Clinical Drug Order/Return Form to:

The A211401 Varenicline/placebo Order Form can be found on the A211401 study page of the Alliance and CTSU websites.

Each bottle will be identified by a unique code number and are not to be designated for use by a specific patient until they have been assigned to a patient by the Alliance Registration Office personnel. After the treatment assignment has been ascertained in the OPEN application, the patient’s study medication code number will be displayed on the confirmation of registration screen.

The treating institution should not have to request additional supplies after a starter supply has been sent. The pharmacy and the Alliance registration office will work together to re-supply each location.

Outdated or remaining drug product should be destroyed on-site per procedures in place at each institution.

IND Status

IND Exempt: Varenicline is IND exempt as used in this trial. This exemption has been determined by attestation that neither the investigator nor sponsor intends to seek a new indication for use or to support any other significant change in the labeling or product advertising for varenicline; this investigation will use an approved route of administration and dosage of varenicline and has no factors that increase the risk of the product; this investigation will be in compliance with 21CFR parts 56, 50, and 312.7; and neither the investigator nor sponsor will promote or represent that varenicline is safe or effective for the context that is under investigation in this study.

Formulation

Commercial varenicline capsular, biconvex tablets contain 0.5 mg (white to off-white, debossed with “Pfizer” on one side and “CHX 0.5” on the other side). Each 0.5 mg varenicline contains 0.85 mg of varenicline tartrate equivalent to 0.5 mg of varenicline free base. The following

inactive ingredients are included in the tablets: microcrystalline cellulose, anhydrous dibasic calcium phosphate, croscarmellose sodium, colloidal silicon dioxide, magnesium stearate, Opadry® White (for 0.5 mg), Opadry® Blue (for 1 mg) and Opadry® Clear.

Storage and Stability

Store at 25°C (77°F); excursions permitted to 15–30°C (59–86°F) (see USP Controlled Room Temperature).

Administration

Varenicline/placebo will be administered at a dosage of 0.5 mg once daily for 3 days, increasing to 0.5 mg twice daily for days 4 to 7, and then to the maintenance dose of 0.5 mg 2 tablets twice daily for up to 12 weeks of treatment. Patients should be instructed to take medication after eating and with a full glass of water.

Drug Interactions

Varenicline is not known to interact with any medications and has no contraindications aside from previous allergic reactions to varenicline.

Other smoking cessation therapies: Safety and efficacy in combination with other smoking cessation therapies has not been established. Coadministration of varenicline and transdermal nicotine resulted in a high rate of discontinuation due to adverse events.

Effect of smoking cessation: Pharmacokinetics or pharmacodynamics of certain drugs may be altered due to smoking cessation with CHANTIX, necessitating dose adjustment.

Pharmacokinetics

- a) Absorption: Varenicline is rapidly absorbed across the gastric mucosa, reaching a peak plasma concentration (C_{max}) in about 4 hours. After multiple oral doses, steady state is reached within 4 days. Bioavailability is unaffected by food or time-of-day dosing (food reduces the incidence and severity of nausea, a common side effect).
- b) Distribution: Varenicline exhibits linear pharmacokinetics after single or repeated doses. Plasma protein binding is low ($\leq 20\%$).
- c) Metabolism: Varenicline undergoes minimal metabolism.
- d) Excretion: Elimination half-life of varenicline is approximately 24 hours. Ninety-two percent of varenicline is excreted unchanged in the urine. Renal elimination of varenicline is primarily through glomerular filtration along with active tubular secretion possibly via the organic cation transporter, OCT2.

Adverse Events

The most commonly reported adverse effects ($>5\%$ and twice the rate seen in placebo-treated patients) of varenicline are nausea (29.4% vs. 10% placebo), insomnia (14.3% vs. 12.4% placebo), abnormal dreams (13.1% vs. 3.5% placebo), headache (12.8% vs. 12.6% placebo), and constipation (9% vs. 1.5% placebo). Nausea is generally mild (72%) to moderate (23%) in intensity, becomes less severe with continued drug use, and causes 2.3% of the subjects to discontinue treatment.

Drug Warnings: The FDA previously required a boxed warning on the varenicline label to alert physicians and subjects to behavior change risks. The labeling warned of the risk of behavioral changes such as: depression, hostility, aggression, suicidal thoughts, suicide, and vehicular crashes. Subjects and family members will be given clear instructions on discontinuing varenicline and alerting study staff in the event such behavior changes occur. This is detailed in the DSMP.

As a result of the black box warning for varenicline, a number of studies have recently (2010-2015) focused on the safety of varenicline in various populations. Studies have included both individual studies with hospitalized smokers and meta-analysis of past randomized clinical trials. The common result in all these studies/reviews is that varenicline is safe and no significant increase in psychiatric conditions was observed in any of these cases. These studies include:

- In 2010, Tonstad reviewed 10 clinical trials comparing varenicline to placebo in over 3091 smokers. Psychiatric disorders (excluding sleep disorders or disturbances) was 10.7% in varenicline and 9.7% in placebo (RR=-1.02 – ns). No cases of suicidal ideation or behavior in the varenicline arms in all 10 trials;[99]
- In 2011, Park et al., conducted a study with 49 smokers who had lung cancer who met with a thoracic surgeon and were given varenicline and counseling or just counseling. The OR was 3.14 (not significant). This study did demonstrate that varenicline is safe (only nausea and abnormal dreams were higher in varenicline arm), and feasible (smokers with lung cancer did adhere to varenicline treatment);[37]
- In 2012, Wong et al., conducted a study with 286 patients who were randomized to varenicline or placebo perioperatively. Relative Risk (RR) was 1.45 for varenicline to help smokers stop smoking. The only significant event was nausea (13.3 vs 3.7, p=0.004);[100]
- In 2013, Nayan et al., reviewed 10 randomized clinical trials and 3 prospective clinical studies of smoking intervention in oncology patients. The interventions included NRT, bupropion and varenicline. The odds ratio (OR) of all interventions was 1.31 to 1.54 (not significant) depending on follow up period. But when the interventions were delivered perioperatively, the OR was significant at 2.31, thereby demonstrating that surgery does present the teachable moment in oncology patients;[101]
- In 2014, Carson et al., conducted a study with 392 hospitalized smokers who were randomized to varenicline vs. placebo for 12 weeks. No increase in psychiatric events were noted, the only increase was nausea (16.3% in varenicline patients vs. 1.5% in counseling alone);[102]
- In 2015 two studies took place, both with very large number of smokers:
 - Thomas et al. – meta-analysis of 39 randomized trials (10,761 pts.) using varenicline vs. placebo to evaluate the incidence of neuropsychiatric events. No increase of suicide, attempted suicide, suicidal ideation, depression, irritability, aggression, or death. There was evidence of reduced anxiety and increase in sleep disorders, insomnia and abnormal dreams and fatigue.[103]
 - Kotz et al. – A review of 753 general practices in England which identified 164,766 smokers who received prescription to stop smoking (106,759 NRT; 6557 bupropion; 51,450 varenicline). Neither bupropion nor varenicline showed any increase in cardiovascular or neuropsychiatric events (including depression and self-harm) compared to NRT (Hazard Ratio (HR)= 0.80), cerebral infarction (HR=0.62), heart failure (HR=0.61), arrhythmia (HR=0.73) or self-harm (HR=0.56).[104]

Weight Gain: Varenicline does not attenuate weight gain after stopping smoking.

Abuse Potential: The manufacturer’s data, available in the package insert, suggests that varenicline is not likely to be abused. The FDA did not classify varenicline as a controlled substance.

Pregnancy Risk: Varenicline is FDA Pregnancy Class “C” drug defined as “Either studies in animals have revealed adverse effects on the fetus (teratogenic or embryocidal or other) and there are no controlled studies in women or studies in women and animals are not available. Drugs should be given only if the potential benefit justifies the potential risk to the fetus.” Since we do not know the potential benefits, we cannot determine the risk-benefit ratio and will, therefore, exclude pregnant individuals at the beginning and during the study. Not enough medical information exists to know what the risks might be to a breast-fed infant so we will exclude individuals who are breast-feeding.

Nursing Guidelines

1. Be aware of black box warning regarding behavior changes, including depression, hostility, aggression, suicidal thoughts, and vehicular crashes. Warn patients of this risk and instruct patients to report any changes in mood or behavior to the study team.
2. Patients may experience nausea. Nausea may improve with time. Treat symptomatically and monitor for effectiveness.
3. Warn of difficulty sleeping and/or unusual dreams.
4. Headache may occur. Treat symptomatically and monitor for effectiveness.
5. Patients may experience mild constipation, encourage increased fluid intake and treat symptomatically as necessary.

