We found that *CHRNA5-CHRNA3-CHRNA4* variants predict age of smoking cessation, age of lung cancer diagnosis, and response to smoking cessation treatments. In a recent meta-analysis, we found that the *CHRNA5* variant rs16969968 is a marker of delayed smoking cessation and accelerated lung cancer diagnosis. The median age of smoking cessation for those with the high-risk variants (AA) at rs16969968 is 56 years versus 52 years for those with the low-risk variants (GG). Similarly, those with the high-risk variants have a 4-year earlier age of lung cancer diagnosis (61 years) compared to those with the low-risk variants (65 years) (Chen et al, in press, JNCI). This can be clinically significant given the high mortality following a diagnosis of lung cancer (50% die within a year of diagnosis and a 5-year survival rate of 16.6%). In clinical trials, those with high-risk genetic variants had more difficulty quitting without treatment, but this genetic risk was ameliorated by aggressive pharmacological treatment (Fig. 1) [70] (please also add reference Bergen et al, 2013)

These results revealed a statistically significant interaction between the genetic variants and pharmacologic treatment. The clinical impact of this genetic and treatment interaction is exemplified by the number needed to treat (NNT), the number of patients who must be treated to prevent one additional bad outcome (e.g., relapse). For example, if a drug has an NNT of 10, it means one would need to treat 10 people with the drug to achieve smoking abstinence in one person. In this smoking cessation trial,[70] the overall NNT to prevent one relapse was 7, supporting the established effect of pharmacotherapy. However, the NNT varied widely depending on haplotype: the NNT was 4 for smokers with the high-risk haplotype (H3) versus >1000 for smokers with the low-risk haplotype (H1). This large difference in NNT was the first finding that genetic variants in the chromosome 15 region interact with treatment for smoking cessation.

Given the existing evidence that this *CHRNA5* variant predicts accelerated risk for lung cancer and favorable response to cessation pharmacotherapy, these findings underscore the potential clinical and public health importance of rs16969968 in *CHRNA5* in relation to smoking cessation treatments.

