3.1 On-Study Guidelines

This clinical trial can fulfill its objectives only if patients appropriate for this trial are enrolled. All relevant medical and other considerations should be taken into account when deciding whether this protocol is appropriate for a particular patient. Physicians should consider the risks and benefits of any therapy, and therefore only enroll patients for whom this treatment is appropriate.

Although they will not be considered formal eligibility (exclusion) criteria, physicians should recognize that the following may seriously increase the risk to the patient entering this protocol:

- Psychiatric illness which would prevent the patient from giving informed consent.
- Medical condition such as uncontrolled infection (including HIV), uncontrolled diabetes mellitus or cardiac disease which, in the opinion of the treating physician, would make this protocol unreasonably hazardous for the patient.
- Patients with a “currently active” second malignancy other than non-melanoma skin cancers or cervical carcinoma in situ. Patients are not considered to have a “currently active” malignancy if they have completed therapy and are free of disease for ≥ 3 years.
- Patients who cannot swallow oral formulations of the agent.

In addition:

- Women and men of reproductive potential should agree to use an appropriate method of birth control throughout their participation in this study due to the teratogenic potential of the therapy utilized in this trial. Appropriate methods of birth control include abstinence, oral contraceptives, implantable hormonal contraceptives or double barrier method (diaphragm plus condom).

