3.2 Eligibility Criteria

Use the spaces provided to confirm a patient’s eligibility by indicating Yes or No as appropriate. It is not required to complete or submit the following pages.

When calculating days of tests and measurements, the day a test or measurement is done is considered Day 0. Therefore, if a test were done on a Monday, the Monday four weeks later would be considered Day 28.

- ___ **3.2.1** Eligible patients will have either confirmed or suspected new diagnosis of lung cancer and have sought a surgical consult relating to this diagnosis.
- ___ **3.2.2** Surgery must be scheduled no sooner than 10 days after randomization and no more than twelve weeks after randomization
- ___ **3.2.3** Have smoked daily or nearly every day in the previous 6 months up to the date of surgical consult AND have smoked at least one puff in the previous 7 days.
- ___ **3.2.4** Motivated to stop smoking, as indicated by a score of 6 or above on the Contemplation Ladder (see Appendix III).76

- ___ **3.2.5** Within the 30 days before registration, no use of: 1) any pharmacologic treatment for smoking cessation, including bupropion or nicotine replacement therapy; 2) any nicotine delivery system (i.e., e-cigarettes and vape products); or 3) be enrolled in any formal behavioral treatment program for tobacco dependence as determined by patient report.
- ___ **3.2.6** No allergies to and not currently using varenicline.
- ___ **3.2.7** No suicidal thoughts as indicated by a positive (1+) response to question 9 on the PHQ9.
- ___ **3.2.8** No active untreated clinically significant psychiatric condition (psychosis, bipolar disorder, or depression).
- ___ **3.2.9** Negative pregnancy test (serum or urine) done ≤ 7 days prior to registration, for women of childbearing potential only.
- A female of childbearing potential is a sexually mature female who: 1) has not undergone a hysterectomy or bilateral oophorectomy; or 2) has not been naturally postmenopausal for at least 12 consecutive months (i.e., has had menses at any time in the preceding 12 consecutive months).
- ___ **3.2.10** No unstable angina, myocardial infarction, or coronary angioplasty within the past 3 months or an untreated cardiac dysrhythmia.
- ___ **3.2.11** No history of seizures.
- ___ **3.2.12** No unstable neurologic, hepatic, renal, cardiovascular, lymphatic, or metabolic disease.
- ___ **3.2.13** Not currently on renal dialysis or has a history of significant renal impairment.

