- ___ **3.2.14** No recent history (≤ 90 days) of substance abuse (outside of tobacco) defined by NIAAA [77] as:
- If male, drinking >14 alcoholic beverages per week for past 1 month.
 - If female, drinking >7 alcoholic beverages per week for past 1 month.
 - Use of cocaine, heroin, club drugs (i.e., MDMA/“ecstasy”), methamphetamine, or hallucinogens (e.g., LSD) at any time during the past 1 month.
 - Use of marijuana on a weekly basis for the past 1 month.
- ___ **3.2.15** Patients must be able to complete study questionnaires in English.
- ___ **3.2.16** ≥ 18 years of age
- ___ **3.2.17** No other household member or relative participating in the study.
- ___ **3.2.18** No known history of any condition or factor judged by the investigator to preclude participation in the study or which might hinder study adherence.
- ___ **3.2.19** Calculated creatinine clearance ≥ 30 mL/min.

Creatinine clearance (CrCl) will be calculated using the Cockcroft-Gault equation as follows:

$$\text{CrCl (ml/min)} = \frac{(140 - \text{age}) \times \text{actual wt (in kg)}}{72 \times \text{serum creatinine (mg/dL)}}$$

For females, use 85% of calculated CrCl value

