4.6 Treatment Assignments and Blinding

Patients will be randomized 1:1 to receive one of two blinded treatments:

Intervention Group: Participants will receive varenicline for 12 weeks plus a brief no-smoking message from the surgical team and behavioral support provided by a telephone smoking quitline (NCI's [name]).

Control Group: Participants will receive placebo for 12 weeks plus a brief no-smoking message from the surgical team and behavioral support provided by a telephone smoking quitline (NCI's [name]).

After the treatment assignment has been ascertained in the OPEN application, the patient's study medication code number will be displayed on the confirmation of registration screen.

The pharmacist or designated contact person at the treating site will maintain records that indicate the identity of the patient and their corresponding study medication code number.

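### Section 10.1 excludes breast-feeding individuals, but none of the 19 eligibility items in Section 3.2 says so

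*Combined protocol and SAP*

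**What the plan says.** The Pregnancy Risk paragraph of Section 10.1 makes two exclusions. Pregnant individuals are excluded at the start and throughout. For breast-feeding, the risk to the infant is unknown and the rule is flat: "we will exclude individuals who are breast-feeding".

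Section 3.2 is the formal list, items 3.2.1 to 3.2.19. Sites are told to use it to confirm "eligibility by indicating Yes or No as appropriate". The nearest item is 3.2.9, which begins "Negative pregnancy test (serum or urine) done" and applies only to women of childbearing potential. Item 3.2.18 is a general clause covering "any condition or factor judged by the investigator to preclude participation in the study".

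Section 3.1 advises physicians to "only enroll patients for whom this treatment is appropriate". It then names four risk conditions, introduced by "Although they will not be considered formal eligibility (exclusion) criteria", and adds advice on contraception. Breast-feeding is not mentioned.

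**The concern.** A rule that the sponsor states without conditions in the drug section is missing from the list that decides who may be registered. Three other parts of the protocol give that list its force:

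- Section 3.0 says the study chair cannot waive eligibility requirements.
- Section 4.4 has staff verify, before registration, that the eligibility criteria are met.
- Section 12.2 defines an ineligible participant as one who fails any of those criteria.

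A site working from Section 3.2 alone could register a breast-feeding patient and find nothing specific there that makes her ineligible. If she were allocated to varenicline, her infant could be exposed to a risk the sponsor chose not to take. The stake is individual safety, not the trial's result.

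**Working it through.** The plan gives no figure to reproduce on this point. The check is a comparison of texts, followed by a bound on how many patients could be affected.

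**Count of items.** Section 3.2 runs from 3.2.1 to 3.2.19 with unbroken numbering and no redaction. Items that mention breast-feeding or lactation: 0 of 19.

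**Where each Section 10.1 exclusion is carried forward.**

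| Place | Pregnancy | Breast-feeding |
|---|---|---|
| Front-page eligibility summary (visible text) | yes | no |
| Section 3.2 | yes (3.2.9) | no |
| Section 5.0, study calendar | yes (test before registration) | no |
| Section 8.2.10, stopping treatment | yes | no |

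The two exclusions stand in consecutive sentences of Section 10.1. One is carried into all four places and the other into none, which looks like an oversight rather than a decision.

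**Whether another item covers it.**

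- Item 3.2.9 does not. A pregnancy test does not detect lactation, and the item's definition of childbearing potential does not address it.
- Item 3.2.18 permits exclusion but does not require it. The Drug Interactions text in Section 10.1 also says varenicline has no contraindication other than prior allergy to it, so an investigator relying on that text might see no reason to use 3.2.18.
- Section 3.1 gives general advice and does not name breast-feeding.

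**Whether the case can arise.** Entry is from age 18 (3.2.16), and 3.2.9 provides a test for women of childbearing potential, so such women are eligible.

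**Upper bound on patients.** Inputs:

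- Women in planned accrual (Section 13.11): 462 + 8 = 470 of 783, and 470/783 = 60.0%. This ignores age, so it is a ceiling.
- Allocation (Section 4.6): "Patients will be randomized 1:1 to receive one of two blinded treatments", so half of those registered are expected on varenicline.
- Dosing (Section 7.4): days 1 to 84.
- Share of women breast-feeding, *p*: not in the documents. An illustrative range of 0% to 0.5% is assumed.

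Expected number registered = 470 × *p*. Expected number on varenicline = 470 × *p* / 2.

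| Assumed *p* | Registered | On varenicline |
|---|---|---|
| 0% | 0 | 0 |
| 0.1% | 0.47 | 0.24 |
| 0.5% | 2.35 | 1.18 |

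The decimals only show the arithmetic. The usable reading is 0 to about 2 registered and 0 to about 1 on active drug. Section 1.1.4 quotes ages at lung cancer diagnosis of 61 and 65 years by genotype. Those ages are not a forecast for this trial, but they suggest that most patients will be past childbearing age, which favours the lower end.

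**The case against.** Section 10.1 belongs to the same protocol and is worded as a firm rule, and nothing in Section 3.2 contradicts it. The front-page summary sends readers to the full text for complete eligibility. An investigator who reads Section 10.1 together with 3.2.18 and Section 3.1 has a clear answer. The Section 3.2 pages need not be completed or submitted, so the list is not a mandatory form. The title pages, consent pages, case report forms and registration screens were not available for this check, and any of them might ask about breast-feeding. The assumed share has no source in the documents, and the true number may well be zero.

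Most of this stands as a limit on weight. The gap is an omission rather than two opposed instructions, other safeguards cannot be ruled out, and the patient counts are only illustrative. It does not remove the point. Sections 4.4 and 12.2 tie registration and ineligibility to the eligibility criteria whether or not the pages are filed. A rule found only in the drug section is easily missed when those criteria are checked. Nothing on the pages not seen would change what Section 3.2 contains.

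**Conclusion.** The inconsistency is real: Section 10.1 states the exclusion and 0 of 19 items in Section 3.2 carry it. Followed as written, and with investigator judgement not exercised, the list would admit a patient whom the sponsor intends to exclude. The practical size is very small: possibly no patients, and about 2 registered and 1 on varenicline at the top of the assumed 0% to 0.5% range. That bound treats all 470 planned women as if age did not matter, and it assumes no safeguard outside the text examined. The point is minor but worth correcting, because the rule protects an infant.

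**What to change.** Add *Not breast-feeding* to Section 3.2 as a statement of its own, for example beside 3.2.9. Keeping it separate means it is not limited by the wording on pregnancy tests and childbearing potential. Make the matching change to the pregnancy line in the front-page summary, unless the pages not seen already contain it.

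The cost is one line in Section 3.2 and a few words on the front page. No new test or visit is needed, and the policy does not change, since the sponsor's existing decision is only moved to where eligibility is checked.
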